6.0 STUDY INTERVENTION(S) AND CONCOMITANT THERAPY

Study intervention is defined as any investigational intervention(s), marketed product(s), placebo, or medical device(s) intended to be administered to a study participant according to the study protocol.

6.1 Study Intervention(s) Administered

Study interventions are summarized in Table 4. For full information regarding the administration of study intervention and the contents of the kit, refer to the Pharmacy Manual. The full instructions for administration of sham are also described in the Pharmacy Manual.

Table 4:Protocol KS301P106: Study Interventions

Group Name	А	В
Intervention Name	KSI-301 5 mg	Sham
Туре	Biological medicinal product	Sham
Dose Formulation	Sterile liquid for intravitreal injection in single-use vials	Empty vial
Unit Dose Strength(s)	mg/mL (based on antibody mass)	N/A
Dosage Level(s)	5 mg	N/A
Route of Administration	Intravitreal injection	Sham injection
Use	Experimental	Sham (to maintain study masking)
IMP and NIMP	IMP	NIMP
Sourcing	Provided centrally by the Sponsor	Provided centrally by the Sponsor
Storage	In the original packaging, as provided, until the time of use. Store at 2-8°C before use. Refer to Pharmacy Manual for additional instructions.	In the original packaging, as provided, until the time of use. Store at 2-8°C before use. Refer to Pharmacy Manual for additional instructions.
Packaging and Labeling	KSI-301 will be provided in vials that will be labeled as required per country requirement.	Sham will be provided in vials that will be labeled as required per country requirement.
Reconstitution and Handling	KSI-301 is an aqueous solution that is provided in vial and filled into a syringe by unmasked site personnel without reconstitution or dilution.	Sham is provided as empty glass vials, which will remain empty throughout the sham treatment procedure. A sham injection mimics an intravitreal injection. It involves pressing the blunt end of an empty syringe, without a needle, against an anesthetized eye.
Current/Former Name(s) or Alias(es)	N/A	N/A

6.2 Preparation/Handling/Storage/Accountability

6.2.1 Preparation, Handling, and Storage

KSI-301 is an aqueous solution provided in vials and filled into syringes by unmasked site personnel without reconstitution or dilution.

Study drug kits must be stored in a secure refrigerator at a controlled temperature of 2°C to 8°C. All study drug vials should be stored in the original packaging, as provided, until the time of use.

Please refer to the Pharmacy Manual for additional instructions.

6.2.2 Study Intervention Accountability and Reconciliation

Study intervention packaging will be overseen by the Sponsor or its designee and bear a label with the identification required by local law, the protocol number, drug identification, and dosage. The packaging and labeling of the study medication will be in accordance with local regulations.

The investigational site will acknowledge receipt of the study intervention, to confirm the shipment condition and content. Any damaged shipments will be replaced. Upon arrival of the study intervention at the site, site personnel will complete the following:

- Check the shipment for damage.
- Verify proper identity, quantity, integrity of seals and temperature conditions and document receipt in IRT system.
- Report any deviations or product complaints to the Sponsor or its delegate upon discovery. Any study intervention under investigation for integrity or temperature excursion should be quarantined in the IRT, and not used until the final assessment by the Sponsor or its designee.

The Investigator or designee must confirm appropriate temperature conditions have been maintained during transit for all study treatment received and any discrepancies are reported and resolved before use of the study treatment.

Only participants enrolled in the study may receive study intervention and only authorized site staff may supply or administer study intervention. All study intervention must be stored in a secure, environmentally controlled, and monitored (manual or automated) area in accordance with the labeled storage conditions with access limited to the Investigator and authorized site staff.

The Investigator, institution, or the head of the medical institution (where applicable) is responsible for study intervention accountability, reconciliation, and record maintenance (i.e., receipt, reconciliation, and final disposition records).

Further guidance and information for the final disposition of unused study interventions are provided in the Pharmacy Manual.

The pharmacist responsible for dispensing study treatment, or the designated site personnel, will select the correct study intervention as assigned through the IRT. Detailed stepwise instructions for the preparation of KSI-301 or sham for administration, mandatory materials to be used, and pre-treatment and post-treatment procedures are detailed in the Pharmacy Manual.

For more detailed information on the formulation, preparation, and handling of KSI-301 and sham, see the Pharmacy Manual.

6.3 Measures to Minimize Bias: Randomization and Masking

6.3.1 Randomization

All participants will be centrally assigned to a randomized study intervention using an IRT system. Before the study is initiated, login information and directions for the IRT will be provided to each site.

Study intervention will be dispensed at the study visits, as summarized in the SoA (Section 1.3).

6.3.2 Masking and Unmasking

This is a double-masked study. There must be a minimum of two Investigators per site to fulfill the masking requirements of this study, as follows:

- **Masked Evaluating Physician(s)**: At least one Investigator will be designated as the evaluating physician who will be *masked* to participants' treatment assignments and will evaluate all ocular assessments (other than the immediate post-injection assessment done by unmasked personnel, as described below).
- Unmasked Treating Physician(s): At least one other Investigator will be designated as the treating (injecting) physician who will be *unmasked* to participants' treatment assignments and will administer study intervention (KSI-301 or sham). This physician or an unmasked assistant will also conduct the immediate post-injection assessments, including tonometry, in the Study Eye (Section 8.1.4). The unmasked treating physician and unmasked staff must not divulge treatment assignment to anyone.

As shown in Section 6.1, there are two study interventions: (1) KSI-301 (the investigational medicinal product); and (2) sham (for which an injection procedure is simulated but not actually performed). The two study interventions are provided are provided in unmasked vials within masked cartons (also referred to as kits), as follows:

• **Masked Cartons**: All study interventions are provided in cartons that are identical in appearance and weight, making them indistinguishable from each other.

Each carton is labeled with an identical carton label that includes a unique kit number. The IRT system will direct site personnel which specific carton to pull from inventory and use for

a specific participant at a given visit based on the unique kit number printed on the carton label and that participant's treatment at that given visit.

• Unmasked Vials Within the Masked Cartons: Owing to differences among vials, syringes, dose-preparation procedures, and treatment procedures that cannot be masked, the treating (injecting) physician is unmasked to study treatment as are any assistants to the treating (injecting) physician. Only unmasked site staff are allowed to open the masked cartons.

Participants, study site personnel (except for the treating physician(s), assistant(s), and pharmacist if any), the designated evaluating physician(s), central reading center personnel, and the Sponsor and its agents will be masked to treatment assignment.

The visual acuity (VA) examiner (performing the refraction, BCVA examination) will be masked to the participant treatment assignment. The BCVA examiner will have no access to the VA scores of a participant's previous visits and may have access only to a participant's refraction data from previous visits.

A participant's treatment assignment will not be unmasked until the end of the study or unless medical treatment of the participant depends on knowing the study treatment the participant received. Emergency code break is available to the Investigator online in the IRT. If unmasking is necessary for participant management (for example, in the case of an SAE for which participant management might be affected by knowledge of the treatment assignment), the Investigator will be able to break the treatment code by accessing the IRT system. Treatment codes must not be broken except in emergency situations. If the Investigator wishes to know a participant's treatment assignment for any other, non-emergency reasons, he or she should consult with the medical monitor. The Investigator should document and provide an explanation for any non-emergency unmasking (for example, accidental unmasking).

For regulatory reporting purposes and if required by local health authorities, the Sponsor or its agents (e.g., contract research organization (CRO) pharmacovigilance personnel) will break the treatment code for all serious, unexpected suspected adverse reactions (SUSARs) that are considered by the Investigator or Sponsor to be related to study intervention. The participant may continue to receive treatment, and the Investigator, participant, and Sponsor or CRO personnel, except for the Pharmacovigilance personnel who must have access to participant treatment assignments to fulfill their roles, will remain masked to treatment assignments.

Additional information regarding masking and unmasking will be outlined in the Masking Manual.

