9.3 Analysis Sets

Population	Description	
Randomized/ Intent to Treat (ITT) Set	The ITT set will consist of all participants who were randomized into one of the study arms.	
	For analyses based on this population, participants will be grouped according to the study intervention assigned at randomization.	
Evaluable/Per Protocol (PP) Set	The PP set will consist of all ITT participants who fulfill all inclusion/exclusion criteria and have no significant protocol deviations that are expected to have a significant impact on the assessment of efficacy, including lack of compliance with study treatment, missing data, and having taken any prohibited medication. All analyses using the PPS will group participants according to the study intervention they received.	
Safety Set	All participants randomly assigned to study intervention and who receive at least one dose of study intervention. Participants will be analyzed according to the intervention they received.	
Pharmacokinetic/Biomarker/ADA Evaluable Set	The PK/biomarker evaluable data set will consist of all participants in the ITT Population with at least one post-Day 1 evaluable sample. The ADA evaluable data set will consist of all participants in the ITT Population with at least one evaluable sample.	

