9.4.1 General Considerations

At Day 1, participants will be randomized 1:1 into one of two treatment arms:

- Group A: KSI-301 5 mg via intravitreal injection at Day 1, Week 8, Week 20, and every 24 weeks thereafter through Week 92.
- Group B: Sham injections at Day 1, Week 8, Week 20, and every 24 weeks thereafter through Week 92.

CONFIDENTIAL

This study is divided into two efficacy and safety assessment periods (Section 1.2), as follows:

- Year 1: from baseline to Week 48; and
- Year 2: from Week 52 to Week 100.

At Week 48, the primary endpoint (the proportion of eyes improving ≥ 2 steps on DRSS from baseline at Week 48) will be compared between the KSI-301 5 mg treatment group and sham using the CMH method

Missing values post-baseline will be imputed using the last observation carried forward (LOCF) procedure. If a participant develops a sightthreatening complication due to DR (DME, PDR, or ASNV), a color fundus photograph for DRSS grading will be obtained and submitted to the reading center at the time of diagnosis, and DRSS scores collected subsequently will be censored. Baseline will be carried forward if all post-baseline observations are missing.

Analysis of data for the first period of the study will be performed when all participants have either completed the Week 48 visit or have discontinued from the study, all data have been entered into the database, cleaned, and verified as appropriate, and the database has been locked.

Likewise, analysis of data for the second period of the study will be performed when all participants have either completed the Week 100 visit or have discontinued from the study, all data have been entered into the database, cleaned, and verified as appropriate, and the database has been locked.

Details of all preplanned analyses, including alternative imputation approaches for the handling of missing data, subgroup analyses (for example, across key demographic and ocular baseline characteristics), and sensitivity analyses, will be included in the SAP. The results of all analyses detailed in the SAP will appear in the final clinical study report.

9.4.2 **Primary Endpoint(s)**

Unless stated otherwise, all analyses described will be performed on the ITT population.

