5.4.1 Full Analysis Set

The Full Analysis Set (FAS) includes all patients who received any study treatment (KSI-301 or sham) and have gradable DRSS value at baseline. Patients will be analyzed according to their randomized treatment. The FAS will be used in the primary analyses of efficacy.

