7.1.2 Analysis of Primary Efficacy Endpoint

The primary efficacy endpoint will be estimated based on the FAS, i.e., all randomized subjects who received at least one treatment injection and have gradable DRSS value at baseline.

The statistical analysis will be performed using the Cochran-Mantel-Haenszel (CMH) method,

A 'Hypothetical' strategy will be applied for all intercurrent events where measurements after occurrence of intercurrent event will be imputed using the last observation carry forward (LOCF) procedure. For patients who develop sight-threatening complication(s) and have non-gradable value at their first visit where open-label treatment is administered, the non-gradable values will be imputed as no change from baseline. For patients without intercurrent event, missing and non-gradable values at Week 48 will be imputed using LOCF. Baseline will be carried forward if all post-baseline observations are missing or non-gradable. Non-gradable values are observations where DRSS level is 90.

The p-value will be reported for comparison between KSI-301 and sham groups. In addition, the weighted percentages difference between the KSI-301 and sham (i.e., KSI-301 – sham) and 95.02% CI of the difference will be presented. Percentages are calculated as 100×number of "responders"/number of patients in FAS. Weighted percentages are based on weighted average of observed estimates across strata using CMH weights. The CI are based on the normal approximation to the binomial proportions.

The CMH method as described for the primary efficacy analysis will be used for all sensitivity analyses below.

7.1.3 Sensitivity Analysis 1

In this analysis, a 'Composite' strategy will be applied for all intercurrent events where patients with occurrence of intercurrent event by Week 48 will be considered as non-responders. For patients without intercurrent event, missing and non-gradable values at Week 48 will be imputed using LOCF, and baseline will be carried forward if all post-baseline observations are missing or non-gradable as in the primary analysis.

7.1.4 Sensitivity Analysis 2

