10.0 SUMMARY OF CHANGES IN THE CONDUCT OF THE STUDY OR PLANNED ANALYSES

The Week 100 analyses will not be performed per protocol, since the study was discontinued early by the Sponsor.

In this SAP, the Sponsor has defined the primary estimand, analysis populations, and strategies for addressing intercurrent events, missing data, and a set of sensitivity analyses for the primary efficacy outcome. Where relevant, these definitions take precedence over those defined in the study protocol.

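### The SAP's primary efficacy set leaves out randomized participants who are never dosed; the doses are given by staff who know the arm, and no planned analysis puts these participants back.

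*Protocol*

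**What the plan says.** **Population.** Protocol 9.3 defines the ITT set: "The ITT set will consist of all participants who were randomized into one of the study arms". Protocol 9.4.2, on the primary endpoint, adds: "Unless stated otherwise, all analyses described will be performed on the ITT population". Section 9.4.3 repeats this for the secondary endpoints.

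SAP 5.4.1 substitutes a set that "includes all patients who received any study treatment (KSI-301 or sham) and have gradable DRSS value at baseline". SAP 7.1.2 describes the primary analysis population as "all randomized subjects who received at least one treatment injection and have gradable DRSS value at baseline", and SAP 7.2 uses the same set for the three key secondary endpoints. SAP Section 10 says of its own definitions: "Where relevant, these definitions take precedence over those defined in the study protocol". SAP Section 1 promises that changes from the protocol's methods will be explained in Section 10. That section says that analysis populations have been defined, but not that all-randomized became treated-only, or why.

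**Who gives the dose.** Randomization takes place on Day 1 (Protocol 1.1), the visit of the first dose (Protocol 1.3.1). Only unmasked staff may open the carton, and Protocol 6.3.2 states that "the treating (injecting) physician is unmasked to study treatment as are any assistants to the treating (injecting) physician". On the sham, Protocol Table 4 (Section 6.1) says: "It involves pressing the blunt end of an empty syringe, without a needle, against an anesthetized eye".

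**When treatment is withheld.** The interruption criteria in Protocol Table 5 (Section 7.1.1) refer to study treatment and do not distinguish the arms.

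**The concern.** Restricting the primary set to treated participants is usually defended on the ground that knowledge of the assignment cannot have influenced whether a participant was treated. That defence is not fully available here. FAS membership depends on a step after randomization that is carried out by people who know the arm, and the two procedures differ in invasiveness. If a randomized KSI-301 participant is never injected, that participant leaves the primary analysis. Under the protocol's ITT rule, the same participant would stay in the denominator and, without post-baseline images, count as a non-responder. Loss of this kind confined to the KSI-301 arm raises that arm's responder rate. The set also serves the three key secondary endpoints, which are tested hierarchically after the primary at the 4.98% level, so a primary result that turned on the choice of set would decide whether they are tested at all.

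**Working it through.** **Inputs**
- About 120 participants per arm (Protocol 9.2, SAP Section 9).
- Two-sided significance level 0.0498 for the primary test (SAP 7.1.1.3).
- Baseline carried forward when no post-baseline DRSS exists (SAP 7.1.2), which makes the participant a non-responder.
- The assumed responder rates and dropout rate are not visible in the public documents, so the figure of 240 cannot be reproduced. It is not disputed here.
- The documents give no number of never-dosed participants. The rates and counts (k) below are assumptions.

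**Step 1: does any planned analysis restore the never-dosed?**
- Sensitivity Analysis 1 (SAP 7.1.3) changes only how intercurrent events are handled.
- Sensitivity Analysis 2 (7.1.4) removes participants with certain deviations.
- Sensitivity Analysis 3 (7.1.5) removes participants with a baseline level other than 47 or 53.
- Disposition tables (6.1) report the numbers randomized and in the FAS by arm, so exclusions will be visible but not analysed.

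None returns to all randomized participants.

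**Step 2: shift in the KSI-301 responder rate.** Let k of 120 KSI-301 participants be never dosed, all non-responders, with no never-dosed participants in the sham arm. If the FAS rate is p, the all-randomized rate is p × (120 − k)/120. At an assumed p = 40%:

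| k | FAS rate | All-randomized rate | Shift (points) |
|---|---|---|---|
| 1 | 40.0% | 40 × 119/120 = 39.7% | 0.3 |
| 3 | 40.0% | 40 × 117/120 = 39.0% | 1.0 |
| 6 | 40.0% | 40 × 114/120 = 38.0% | 2.0 |

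The shift is p × k/120, so it scales with the rate. At p = 25% it is 0.42 points for k = 2 and 1.25 for k = 6. At p = 45% it is 0.75 and 2.25.

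**Step 3: can it change the primary conclusion?** The strata in SAP 7.1.2 are not visible, so this uses an unstratified pooled z-test: z = (x1/n1 − x0/n0) / √[p̄(1 − p̄)(1/n1 + 1/n0)], with p̄ = (x1 + x0)/(n1 + n0).
- 30 KSI-301 responders against 18/120 sham, k = 1. FAS: 30/119 = 25.2% against 15.0%, z = 1.970, p = 0.0488. All randomized: 30/120 = 25.0% against 15.0%, z = 1.936, p = 0.0528.
- 22 KSI-301 responders against 12/120 sham, k = 5. FAS: 22/115 = 19.1% against 10.0%, p = 0.0467. All randomized: 22/120 = 18.3% against 10.0%, p = 0.0642.
- With 6/120 or 12/120 sham responders, no KSI-301 count crosses 0.0498 for k of 3 or fewer.

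Only results already next to the threshold move across it.

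**Step 4: complication endpoints.** For the first and third key secondary endpoints (SAP 7.2.1 and 7.2.3) the direction can reverse. With x events among 120 − k dosed KSI-301 participants, the FAS rate is x/(120 − k). Adding k participants as event-free gives x/120, which is lower and favours KSI-301. Restoring the never-dosed there needs an explicit counting rule.

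**The case against.** The strongest reply is that never-dosed participants should be very few and that the rules give no opening for arm-dependent dosing. Much of this stands.

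- A reader might infer that a sham may go ahead where a real injection would be withheld. No passage says so. Table 5 applies the same interruption criteria to both arms, so following it would withhold the sham too. Arm-dependence would have to come from discretion or non-adherence by unmasked staff. Protocol 6.3.2 also says only that the unmasked physician administers treatment; it leaves open who decides whether to treat, and gives nearly all ocular evaluation to the masked physician.
- A reader might infer that missing the Day 1 dose removes a participant. It does not. The FAS admits anyone who received any study treatment. Protocol 4.1.3 has missed doses made up at unscheduled visits and schedules further doses at Weeks 8, 20 and 44, and Protocol 7.1.1 allows interrupted treatment to resume. Only participants who are never dosed are lost.
- Eligibility is rechecked on Day 1 (Protocol 5.0), including infection and inflammation, and the participant is masked.
- The unmasked injector is an ordinary feature of a sham-controlled trial and is not itself an error.
- SAP Section 10 discloses that populations were redefined, and the disposition tables will show any imbalance.

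These points limit the likely size. They do not show that never being dosed is independent of arm, supply an all-randomized analysis, or explain the departure from the protocol.

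**Conclusion.** The point holds. The SAP replaces the protocol's all-randomized population with one that requires treatment, the treatment is given by staff who know the arm, and no planned analysis checks the effect of that restriction. A reader might go further and conclude that the randomized comparison is broken. The documents do not support that: they show that selection could depend on arm, not that it does or that it is frequent.

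The effect is probably small: about 0.3 percentage points on the KSI-301 responder rate for each never-dosed participant in that arm, and a changed conclusion only for a borderline result. These figures assume a 40% responder rate, never-dosed participants in the KSI-301 arm only, all counted as non-responders, and an unstratified test. If nobody goes undosed, the choice of set on this point makes no difference.

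**What to change.** 1. In SAP 5.4.1, 7.1.2 and 7.2, define the primary efficacy set as all randomized participants with a gradable baseline DRSS, analysed as assigned. The baseline condition should not depend on arm, because the images are taken at screening and graded by a masked reading center.
2. For the DRSS endpoints, never-dosed participants without post-baseline images are then non-responders under the existing baseline-carried-forward rule. SAP 5.2 and 5.3 anchor study day and baseline on the first dose, so give never-dosed participants the randomization date as their anchor.
3. For the complication endpoints, use any observed follow-up, state how never-dosed participants with none are counted, and add a check that does not assume they are event-free.
4. Keep the treated-only FAS as a sensitivity analysis.
5. List never-dosed participants with reasons by arm.
6. State the change from the protocol's ITT set, and the reason for whichever set is used, in SAP Section 10.

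The cost is one revised definition, one counting rule with its check, and one listing. The sample size is unaffected. The KSI-301 responder rate may be marginally less favourable.
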